4.3 Investigate what predicts switching at 3 months

Analysis: This will be done for all randomized patients who are not missing scores or other predictors of interest. This analysis will be performed using the LASSO for logistic regression where the outcome is switching status (the probability modelled is switching) or 6M HA configuration choice (modelled probability is unilateral). Covariates (denoted generally as L below) to include in these models are age at baseline, gender, pure tone average in the better ear, baseline global HHI-E, baseline APHAB Global, baseline APHAB AV, binaural loudness summation (both), REAfree (Dichotic Digits, free right minus free left), REAdirect (Dichotic Digits, direct right minus direct left), cognitive effect LE (Dichotic Digits, direct left minus free left), cognitive effect RE (Dichotic Digits, direct right minus free right), AWARRM recall, and education-adjusted MoCA total score. The selected variables, their odds ratios, and 95% confidence intervals constructed from post-selection inference methods (R package ‘selectiveInference’) will be reported.

$$\text{Hearing Aid Switching Status} = \beta_0 + \beta_L * L$$

**Table 3: Logistic Regression OR Estimates
Probability Modelled: Switched HA Configuration**

Covariate	OR	P-S 95% C.I.
Covariate 1 (Ref: category)		
Category x....	XXX	(XXX , XXX)
Covariate 2	XXX	(XXX , XXX)

4.4 Describe patient characteristics for those who switch their HA configuration vs. those who don't

Analysis: The characteristics from “non-switchers” will be compared to “switchers” with the use of a “Table 1”. As appropriate, we will present the mean with standard deviation (SD), median with interquartile range (IQR), and ranges (min and max), or frequency with percentage. A similar table will be constructed with participants stratified by 6M HA configuration choice.

Table 4: Patient Characteristics for Non-Switchers and Switchers

	Non-Switchers (N=XXX)	Switchers (N=XXX)
Clinical Site		
Duke	XXX (%)	XXX (%)
Vanderbilt	XXX (%)	XXX (%)
Gender		
Female	XXX (%)	XXX (%)
Male	XXX (%)	XXX (%)
Other	XXX (%)	XXX (%)
Age at Baseline Visit		
N	XXX	XXX

Missing	XXX	XXX
Mean (SD)	XXX (XXX)	XXX (XXX)
Median	XXX	XXX
Q1, Q3	XXX , XXX	XXX , XXX
Range	XXX - XXX	XXX - XXX
Race		
American Indian/Alaska Native	XXX (%)	XXX (%)
Asian	XXX (%)	XXX (%)
Black or African American	XXX (%)	XXX (%)
White	XXX (%)	XXX (%)
More than one race	XXX (%)	XXX (%)
Native Hawaiian/Pacific Islander	XXX (%)	XXX (%)
Declined	XXX (%)	XXX (%)
Ethnicity		
Hispanic or Latino	XXX (%)	XXX (%)
Not Hispanic or Latino	XXX (%)	XXX (%)
Declined	XXX (%)	XXX (%)
Personal Income Last Year		
\$0	XXX (%)	XXX (%)
\$1 to \$9999	XXX (%)	XXX (%)
\$10,000 to \$24,999	XXX (%)	XXX (%)
\$25,000 to \$49,999	XXX (%)	XXX (%)
\$50,000 to \$74,999	XXX (%)	XXX (%)
\$75,000 to \$99,999	XXX (%)	XXX (%)
\$100,000 to \$149,999	XXX (%)	XXX (%)
\$150,000 or greater	XXX (%)	XXX (%)
Prefer not to answer	XXX (%)	XXX (%)
Hearing Aid Health Insurance Benefits		
No	XXX (%)	XXX (%)
Yes	XXX (%)	XXX (%)
Not sure	XXX (%)	XXX (%)
Marital Status		
Married	XXX (%)	XXX (%)
Widowed	XXX (%)	XXX (%)
Divorced	XXX (%)	XXX (%)
Separated	XXX (%)	XXX (%)
Never married	XXX (%)	XXX (%)
Prefer not to answer	XXX (%)	XXX (%)
Living Arrangements		
Alone	XXX (%)	XXX (%)
With spouse	XXX (%)	XXX (%)
With spouse and others	XXX (%)	XXX (%)
Other	XXX (%)	XXX (%)
Prefer not to answer	XXX (%)	XXX (%)

Education

Less than high school	XXX (%)	XXX (%)
High school	XXX (%)	XXX (%)
Some college	XXX (%)	XXX (%)
4-year degree	XXX (%)	XXX (%)
Graduate degree	XXX (%)	XXX (%)
Other	XXX (%)	XXX (%)

Quarter of Baseline Visit

2021 Q2	XXX (%)	XXX (%)
2021 Q3	XXX (%)	XXX (%)
...	XXX (%)	XXX (%)

Total MoCA Score

N	XXX	XXX
Missing	XXX	XXX
Mean (SD)	XXX (XXX)	XXX (XXX)
Median	XXX	XXX
Q1, Q3	XXX , XXX	XXX , XXX
Range	XXX - XXX	XXX - XXX

Pure Tone Average in Better Ear

N	XXX	XXX
Missing	XXX	XXX
Mean (SD)	XXX (XXX)	XXX (XXX)
Median	XXX	XXX
Q1, Q3	XXX , XXX	XXX , XXX
Range	XXX - XXX	XXX - XXX

Hearing Loss Classification in Better Ear

Mild	XXX (%)	XXX (%)
Moderate	XXX (%)	XXX (%)

(report generated on XXXXXXX)

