3.2 Additional Variables of Interest

Variable	Description	Variables and Source	Specifications
----------	-------------	----------------------	----------------

Randomization assignment	hearing aid assignment	assign	Binary 1: unilateral 2: bilateral
Clinical site	Which site - Duke or Vanderbilt?	which_site Character version: which_site_ch	Binary 1: Vanderbilt 2: Duke
GHABP Unaided	Unaided: baseline	Question 2 average, 4 standard scenarios: ghabp_q2_4block_base Question 3 average, 4 standard scenarios: ghabp_q3_4block_base	For questions 2 and 3 (IF they answer yes to question 1), doing this separately by question: 1. Subtract 1, multiply by 25, average answer to question across 4 standard scenarios There are 6 scenarios (4 standard, 2 user-nominated) Note that question 1 just asks if this scenario has happened – participants are only included in the averages if they answer “yes” Lower scores are better for both questions
ECHO	Baseline only Note: this is the “sister” questionnaire to SADL (aided)	Global score: echo_global_base Positive effect subscale: echo_positive_effect_base Service cost subscale: echo_service_cost_base Negative features subscale: echo_negative_features_base Personal image subscale: echo_personal_image_base	Questions 1 – 15 are used. This is scored from 1-7 (or reversed for questions 2, 4, 7, 13). There are 4 subscales: Positive Effect, Service & Cost, Negative Features, Personal Image. For each subscale, the average score is calculated. For the global score, this is the mean of the scores for all items (excluding question 11 if applicable).

			
Higher scores are better (higher expectations).
 
See PCORI Scoring file for more details

TFI	
Tinnitus Functional Index
 
Only at baseline
	
Yes/no: tfiyn
 
Number of TFI questions missing: tfi_num_miss
 
TFI invalid flag: tfi_invalid
 
TFI overall score: tfi_overall_score
	
Non-missing if tfiyn=1
 
Overall score: sum all valid answers, divide by the number of questions with valid answers, multiply by 10
 
If more than 7 items are omitted, the overall score is not valid.
 
8 subscales but only reporting overall score
 
Lower scores are better
 
See PCORI Scoring file for more details

Binaural loudness summation	
Baseline only
 
CSL level right
 
CSL level left
 
CSL level both
	
binaural_r_base
 
binaural_l_base
 
binaural_both_base
	Continuous

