Subscale (Baseline)

N	XXX	XXX
Missing	XXX	XXX
Mean (SD)	XXX (XXX)	XXX (XXX)
Median	XXX	XXX
Q1, Q3	XXX, XXX	XXX, XXX
Range	XXX - XXX	XXX - XXX

SSQ Qualities of Hearing

Subscale (3-Month)

N	XXX	XXX
Missing	XXX	XXX
Mean (SD)	XXX (XXX)	XXX (XXX)

Median	XXX	XXX
Q1, Q3	XXX, XXX	XXX, XXX
Range	XXX - XXX	XXX - XXX
Binaural Loudness Summation:		
Right (Baseline)		
N	XXX	XXX
Missing	XXX	XXX
Mean (SD)	XXX (XXX)	XXX (XXX)
Median	XXX	XXX
Q1, Q3	XXX, XXX	XXX, XXX
Range	XXX - XXX	XXX - XXX
Binaural Loudness Summation:		
Left (Baseline)		
N	XXX	XXX
Missing	XXX	XXX
Mean (SD)	XXX (XXX)	XXX (XXX)
Median	XXX	XXX
Q1, Q3	XXX, XXX	XXX, XXX
Range	XXX - XXX	XXX - XXX
Binaural Loudness Summation:		
Both (Baseline)		
N	XXX	XXX
Missing	XXX	XXX
Mean (SD)	XXX (XXX)	XXX (XXX)
Median	XXX	XXX
Q1, Q3	XXX, XXX	XXX, XXX
Range	XXX - XXX	XXX - XXX
Dichotic Digits: Right Ear Directed (Baseline)		
N	XXX	XXX
Missing	XXX	XXX
Mean (SD)	XXX (XXX)	XXX (XXX)
Median	XXX	XXX
Q1, Q3	XXX, XXX	XXX, XXX
Range	XXX - XXX	XXX - XXX
Dichotic Digits: Left Ear Directed (Baseline)		
N	XXX	XXX
Missing	XXX	XXX
Mean (SD)	XXX (XXX)	XXX (XXX)
Median	XXX	XXX
Q1, Q3	XXX, XXX	XXX, XXX
Range	XXX - XXX	XXX - XXX
Dichotic Digits: Free Recall Both (Baseline)		
N	XXX	XXX
Missing	XXX	XXX
Mean (SD)	XXX (XXX)	XXX (XXX)
Median	XXX	XXX
Q1, Q3	XXX, XXX	XXX, XXX

Range	XXX - XXX	XXX - XXX
Dichotic Digits: Free Recall Right (Baseline)		
N	XXX	XXX
Missing	XXX	XXX
Mean (SD)	XXX (XXX)	XXX (XXX)
Median	XXX	XXX
Q1, Q3	XXX, XXX	XXX, XXX
Range	XXX - XXX	XXX - XXX
Dichotic Digits: Free Recall Left (Baseline)		
N	XXX	XXX
Missing	XXX	XXX
Mean (SD)	XXX (XXX)	XXX (XXX)
Median	XXX	XXX
Q1, Q3	XXX, XXX	XXX, XXX
Range	XXX - XXX	XXX - XXX
Speech and Noise Test: 0 Degrees (Co-located) Score (Baseline)		
N	XXX	XXX
Missing	XXX	XXX
Mean (SD)	XXX (XXX)	XXX (XXX)
Median	XXX	XXX
Q1, Q3	XXX, XXX	XXX, XXX
Range	XXX - XXX	XXX - XXX
Speech and Noise Test: 0 Degrees (Co-located) Score (3-Month)		
N	XXX	XXX
Missing	XXX	XXX
Mean (SD)	XXX (XXX)	XXX (XXX)
Median	XXX	XXX
Q1, Q3	XXX, XXX	XXX, XXX
Range	XXX - XXX	XXX - XXX
Speech and Noise Test: Speech Left, Noise Right Score (Baseline)		
N	XXX	XXX
Missing	XXX	XXX
Mean (SD)	XXX (XXX)	XXX (XXX)
Median	XXX	XXX
Q1, Q3	XXX, XXX	XXX, XXX
Range	XXX - XXX	XXX - XXX
Speech and Noise Test: Speech Left, Noise Right Score (3-Month)		
N	XXX	XXX
Missing	XXX	XXX
Mean (SD)	XXX (XXX)	XXX (XXX)

Median	XXX	XXX
Q1, Q3	XXX, XXX	XXX, XXX
Range	XXX - XXX	XXX - XXX
Speech and Noise Test: Speech Left, Noise Right Change Score		

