GHABP Aided	GHABP is measured at 3 months (aided)	
Question 2 average, 4 standard scenarios: ghabp_q2_4block_3m
 
Question 3 average, 4 standard scenarios: ghabp_q3_4block_3m
 
Question 4 average, 4 standard scenarios: ghabp_q4_4block_3m
 
Question 5 average, 4 standard scenarios: ghabp_q5_4block_3m
 
Question 6 average, 4 standard scenarios: ghabp_q6_4block_3m
	
For questions 3-6 (IF they answer yes to question 1), doing this separately by question:
 
 1. Subtract 1, multiply by 25, average answer to question across 4 standard scenarios 
Note: ignore current question 2 for analyses as it is non-standard but report on this in a descriptive table
 
There are 6 scenarios (4 standard, 2 user-nominated)
 
Note that question 1 just asks if this scenario has happened – participants are only included in the

			
averages if they answer “yes”
 
Higher/lower scores are better depending on question

Binaural loudness summation	Baseline only CSL level right CSL level left CSL level both	binaural_r_base binaural_l_base binaural_both_base	Continuous
Dichotic digit test	Baseline only Right ear directed Left ear directed Free recall both ears Right ear free recall Left ear free recall	dichotic_r_base dichotic_l_base dichotic_free_both_base dichotic_free_r_base dichotic_free_l_base	Continuous
Speech and Noise Test	Baseline (unaided) and 3-months (aided) Speech and noise 0 degrees (collocated) Speech left, noise right Noise left, speech right	
Baseline: sin_collocated_base sin_right_base sin_left_base
 
3-Months: sin_collocated_3m sin_right_3m sin_left_3m
 
Change: sin_collocated_change sin_r_change sin_l_change
 
May also want change scores for speech to aided side and speech to unaided side
	
Continuous
 
Change scores: 3m-baseline for each of collocated, speech left/noise right, noise left/speech right
 
Positive values for unaided/aided variables indicate speech is louder than noise; negative indicate speech is under the noise
 
For unilateral assigned, also have speech to aided side (advantage) and speech to unaided side (disadvantage).
 
Speech to aided (advantage):
 
 • If assigned R, this is noise left, speech right

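### The switching and choice models enter the raw both-ears CSL level under the name binaural loudness summation, so they do not test summation

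*SAP*

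**What the plan says.** In the Hearing Aid Choice and Switching SAP, section 3.2 describes the binaural loudness summation entry as "Baseline only CSL level right CSL level left CSL level both", held in "binaural_r_base binaural_l_base binaural_both_base". The only specification is that the values are continuous. No formula or scoring direction is given, and CSL is not expanded. Section 3.2 of the Secondary (3-Month) SAP has the same entry, including "CSL level both". Table 2 in section 4.2 of that SAP reports the three levels as separate rows, each headed "Binaural Loudness Summation".

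Section 4.3 of the Choice and Switching SAP then fits a LASSO logistic regression to two outcomes: switching at 3 months, and "6M HA configuration choice (modelled probability is unilateral". The candidate list includes "binaural loudness summation (both), REAfree (Dichotic Digits, free right minus free left". Degree of loss enters separately, in "pure tone average in the better ear, baseline global HHI-E". The dichotic-digit predictors are written as explicit subtractions, for example "cognitive effect LE (Dichotic Digits, direct left minus free left".

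**The concern.** Loudness summation is what a second ear adds, so a measure of it has to compare a one-ear level with the two-ear level. The predictor in section 4.3 is the two-ear level alone. The dichotic digits also appear in the variable table as raw continuous scores, but section 4.3 turns them into four stated differences. The loudness measure, in the same sentence, gets no difference.

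It is the only predictor on the list named for a two-ears-versus-one effect, and the protocol's third secondary objective is to explore patients' preference for their final configuration. If the LASSO drops the variable, a report could say that summation does not predict choice. If it is kept, its odds ratio could be printed under a summation label. Neither statement would have been tested.

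**Working it through.** The plan states no figure for this predictor, so there is nothing to reproduce. The check traces the definitions and then illustrates how far a both-ears level can stand in for summation.

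**1. Which variable is entered.** The word *both* in section 4.3 matches one of the three variables in section 3.2, `binaural_both_base`. The two variable tables and the 3-month Table 2 define or list the three levels and nothing derived from them.

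**2. Whether the model can recover the contrast.** If the right, left and both levels were all in the model, their coefficients could combine into mean of right and left minus both. The 13 candidates in section 4.3 include neither `binaural_r_base` nor `binaural_l_base`, so this cannot happen. Better-ear pure tone average (PTA) is at most a partial stand-in for single-ear CSL level.

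**3. How much of the both-ears level is summation.** Let M be the monaural level, S the summation (M minus both) and B the both-ears level, so B = M − S. With M and S independent:

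- share of Var(B) due to S = SD_S² / (SD_M² + SD_S²)
- corr(B, S) = −SD_S / √(SD_M² + SD_S²)

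The SDs below are assumptions.

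- SD_M = 10, SD_S = 2: 4/104 = 0.038, or 4%.
- SD_M = 8, SD_S = 2: 4/68 = 0.059, or 6%; correlation −0.24.
- SD_M = 8, SD_S = 3: 9/73 = 0.123, or 12%; correlation −0.35.
- SD_M = 5, SD_S = 4: 16/41 = 0.390, or 39%.

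PTA in the model removes part of M. If corr(M, PTA) were 0.7, with S independent of PTA, SD_M = 8 and SD_S = 2, the residual variance of M is 64 × (1 − 0.49) = 32.6. The share due to S becomes 4/36.6 = 11%, against 6% without PTA.

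**4. Direction.** Allow corr(M, S) = ρ. Then

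corr(B, S) = (ρ·SD_M − SD_S) / √(SD_M² + SD_S² − 2ρ·SD_M·SD_S).

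With SD_M = 8 and SD_S = 2:

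- ρ = 0: −2/√68 = −0.24
- ρ = 0.3: 0.4/√58.4 = +0.05
- ρ = 0.5: 2/√52 = +0.28

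The sign changes where ρ = SD_S/SD_M = 0.25.

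**5. Overlap with degree of loss.** With r = corr(M, PTA), SD_M = 8 and S independent of PTA, the share of Var(B) explained by PTA is (8r)² / (64 + SD_S²).

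- r = 0: 0
- r = 0.7: 31.4/80 = 0.39 (SD_S = 4) to 31.4/65 = 0.48 (SD_S = 1)
- r = 0.9: 51.8/65 = 0.80 (SD_S = 1)

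The documents report no correlation between CSL level and PTA.

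**The case against.** The both-ears level may be a deliberate choice. Section 4.3 picks one of three recorded levels by name, and the activity log shows that this model was revised after discussion on 11.26.2024. Writing out subtractions for the dichotic digits could mean that the authors subtract where they want a difference. In the 3-month Table 2 the rows are marked right, left and both, so a reader is unlikely to take the right-ear row for a summation value. The 3-month SAP also points to an external variable file, not supplied here, that might define a score. The analysis is exploratory and this is one of 13 candidates.

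Much of this stands as a limit on the size of the point. It does not remove it. A deliberate both-ears level would still be reported under a name for something else. The Notes field of the Choice and Switching SAP is blank, and its loudness entry, unlike its SADL and ECHO entries, does not refer to the scoring file. An unseen file does not settle what section 4.3 tells the analyst to fit.

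The SDs in the illustration are assumed, and the resulting range is about tenfold, so it shows a mechanism and not a trial quantity. The choice between better-ear and mean monaural level as reference is also one that the documents do not settle.

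**Conclusion.** The point holds as a mislabelled predictor. As written, section 4.3 fits a both-ears level, and neither its selection nor its omission would be evidence about summation. That conclusion needs only the SAP's own variable definitions and candidate list. The 4% to 39% share rests on assumed SDs and on independence of monaural level and summation.

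A reader might infer two stronger things, and the documents support neither.

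- **That the sign of the odds ratio runs backwards.** The SAPs give these variables no direction. Even with summation scored as monaural minus both, the marginal sign depends on the correlation between monaural level and summation (step 4). What can be said is that the direction is unstated and could be read in reverse.
- **That the predictor is largely degree of hearing loss.** Step 5 gives anything from 0 to 80%, depending on a correlation that the documents do not report. PTA is also a candidate in the same models, so any overlap can be shared if both are kept, although the LASSO may keep only one.

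This is a cheap improvement to an exploratory analysis. The primary APHAB comparison does not use the variable.

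**What to change.** - In section 3.2 of the Choice and Switching SAP, define a summation variable as one prespecified monaural reference minus `binaural_both_base`. The reference is either the better-ear level or the mean of right and left. State that positive means more summation, and expand CSL so that this direction can be checked.
- In section 4.3, use it in place of `binaural_both_base` in both LASSO models (3-month switching and 6-month choice).
- If the raw level is kept as a predictor, call it CSL level, both ears, and do not interpret it as summation.
- In Table 2 of the 3-month SAP, add a row for the derived variable and relabel the three existing rows as CSL levels.
- The SAP's completion date is December 31, 2024, so the models may already have been run. If so, document the change and report both versions.

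All three levels are already collected. The cost is one derived variable, some wording, and possibly refitting two models.

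### The four dichotic-digit predictors in the switching and final-choice LASSO have rank 3, so for effects along one direction the variables it names depend on unstated scaling and penalty choices

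*SAP*

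**What the plan says.** Section 4.3 of the Hearing Aid Choice and Switching SAP fits a LASSO logistic regression to two outcomes: switching at 3 months and hearing-aid configuration choice at 6 months. The candidate list has 13 predictors. Four come from the dichotic digit test. The list begins with these three: "REAfree (Dichotic Digits, free right minus free left), REAdirect (Dichotic Digits, direct right minus direct left), cognitive effect LE". The last of them is the directed score of the left ear less its free-recall score. The fourth is the same difference for the other ear, given as "cognitive effect RE (Dichotic Digits, direct right minus free right".

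Section 3.2 lists the raw variables as "dichotic_r_base dichotic_l_base dichotic_free_both_base dichotic_free_r_base dichotic_free_l_base". The four predictors use four of these five; the combined free-recall score is not used. The analysis set is complete-case: "This will be done for all randomized patients who are not missing scores or other predictors of interest".

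Table 3 is to show the variables that the LASSO selects, with odds ratios and post-selection 95% intervals. The section does not say whether predictors are standardised or how the penalty is chosen, and it does not mention that the four dichotic measures are related.

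**The concern.** Four pairwise differences of four scores cannot all be independent when they form a closed loop, and these do. A model with all four has one direction along which coefficients can move without changing any predicted probability. Table 3 could then name ear advantage or cognitive effect as a predictor of patient choice although the outcome data do not separate the two descriptions.

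That matters because section 4.3 is the SAP's only multivariable model of switching and 6-month choice; section 4.2 models both outcomes on assigned treatment alone. Protocol secondary objective 3 concerns patient preference for the final configuration, and these two constructs would carry different messages for a clinician.

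**Working it through.** The plan states no figure for this analysis, so there is nothing to reproduce. The dependence follows from the SAP's definitions alone; the sizes below need assumptions.

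**1. Dependence.** Write fR, fL, dR, dL for the free and directed scores of the right and left ear.
- REAfree + CE_RE = (fR − fL) + (dR − fR) = dR − fL
- REAdirect + CE_LE = (dR − dL) + (dL − fL) = dR − fL

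So REAfree − REAdirect − CE_LE + CE_RE = 0. Because the analysis set is complete-case, this holds row by row. In that order the null vector is (1, −1, −1, 1). Rank is 3 of 4, and any three of the four have full rank 3.

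**2. Flat likelihood.** In simulated data (assumed: n = 350; means 85/75/92/84 and SDs 10/14/6/10 for fR/fL/dR/dL; correlation 0.6; only these four predictors in the model), the log-likelihood was −213.392463 at shifts t = −1, 0, 0.05 and 1 along the null vector. A shift of 0.05 multiplies two of the per-10-point odds ratios by exp(0.5) = 1.65 and the other two by exp(−0.5) = 0.61, with no change in fit.

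**3. What the L1 penalty does with raw scores.** With all four active, the penalty must also be flat along the null vector. With coefficient signs (+, −, +, −) its slope is 1 + 1 − 1 − 1 = 0, so it is flat and the solution is not unique. Two solutions from different starting values, at the same penalty (0.001) and the same objective, per 10 points:

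| | REAfree | REAdirect | CE_LE | CE_RE | Sum of absolute values |
|---|---|---|---|---|---|
| First | 0.336 | −0.020 | 0.771 | −0.209 | 1.336 |
| Second | 0.533 | −0.217 | 0.575 | −0.013 | 1.338 (equal up to rounding) |

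The REAdirect odds ratio is exp(−0.020) = 0.98 in one and exp(−0.217) = 0.80 in the other. For CE_RE it is 0.81 and 0.99. Over three assumed drivers and three penalties, 5 of 9 raw-unit fits had all four active and were not unique; the other 4 were unique with two active. A separate set of raw-unit simulations, also on assumed scores, selected all four in 12–28% of runs with one true driver and in 90–100% with a two-variable driver.

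**4. What it does with standardised scores.** The flatness condition becomes a signed sum of the four predictor SDs equal to zero. With the simulated SDs 10.95, 7.49, 11.43 and 7.43, the closest signed sum is 10.95 + 7.49 − 11.43 − 7.43 = −0.42, so all four cannot be active together. All 9 fits were unique, with two or three active.

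**5. Who picks the description.** Take a true effect c × (CE_RE − CE_LE), which is the same quantity as c × (REAdirect − REAfree). With standardised predictors, each description costs c times the sum of its two SDs. Assume correlation 0.6, free-recall SD 7 and directed SD 10.
- REAfree SD = √(2 × 49 × 0.4) = 6.26; REAdirect SD = √(2 × 100 × 0.4) = 8.94; sum 15.20
- CE_LE and CE_RE SD = √(49 + 100 − 2 × 0.6 × 70) = √65 = 8.06 each; sum 16.12

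The ear-advantage pair is cheaper. If instead the right-ear SD is 7 and the left-ear SD is 10, the two sums swap and the cognitive pair is cheaper. Simulation (assumed n = 300, penalty 0.03, 100 runs per row) follows this:

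| Assumed SDs | REAfree / REAdirect selected | CE_LE / CE_RE selected |
|---|---|---|
| All equal | 71% / 75% | 76% / 75% |
| Free 7, directed 10 | 96% / 99% | 44% / 53% |
| Right 7, left 10 | 51% / 46% | 100% / 94% |

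The effect on the outcome has the same form in each row; only the spread of the scores differs.

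**6. A single driver.** With one true predictor (log odds ratio 0.6 per SD, standardised, n = 350, 100 runs each), it was selected in 100% of runs and had the largest coefficient in 99–100%. Each redundant variable was also selected in 14–32%.

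**The case against.** A reader might infer that the analysis cannot tell ear advantage from cognitive effect at all, or that its odds ratios for these measures are not identified. The documents do not support either reading. Non-identification of all four odds ratios belongs to an unpenalised fit of all four. The SAP plans a LASSO and reports only what it selects. With standardised predictors at most three of the four were kept, their odds ratios exist given the selection, and a single true driver was found every time. Even on the redundant direction, the two descriptions are the same quantity, so naming either pair is not an error about patients; what misleads is the construct label.

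It is also fair that section 4.3 is not the only place where choice is examined. Section 4.2 models both outcomes on assignment, section 4.4 describes switchers and non-switchers, and the protocol gives the determinants of choice to focus groups as well. The simulated percentages rest on assumed score distributions and penalties and are not forecasts for this trial.

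Finally, dropping a variable is not free under an L1 penalty. With REAdirect deleted, a true directed-ear effect must be written as REAfree + CE_RE − CE_LE, three coefficients in place of one. In simulations of that case, each cognitive effect was named in 78–97% of runs at a lighter penalty and in only 23–68% at a heavier one; a further set reported both in 95–100%.

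All of this stands and limits the point. It does not remove the dependence, the silence on scaling and penalty, or the singular refit that can occur in raw units.

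**Conclusion.** The concern holds in limited form. The rank deficiency is exact and rests only on the SAP's definitions. Its consequence is confined to effects that combine predictors along one direction. There, the selected variables and their odds ratios are settled by scaling and penalty, not by how well the outcome data support one description over the other. If scores stay in raw units, the solution may not be unique, and selection of all four makes the refit and post-selection intervals singular. If predictors are standardised, that failure was not seen, but the choice of label still follows the spread of the scores.

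How often either happens depends on score SDs, correlation and penalty, which the documents do not give. The other nine predictors do not alter the identity among these four. This is an exploratory analysis: no randomised comparison, and in particular not the primary APHAB comparison, is affected. The change is worth making because it is small and the defect is certain.

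**What to change.** In SAP section 4.3, for both the 3-month switching model and the 6-month choice model:

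- Replace the four dichotic measures with one pre-specified set of three, chosen on construct grounds before fitting. One symmetric option is A = (REAfree + REAdirect)/2, B = (CE_LE + CE_RE)/2 and D = REAdirect − REAfree. All four are recoverable: REAfree = A − D/2, REAdirect = A + D/2, CE_LE = B − D/2, CE_RE = B + D/2. Any three of the four would also remove the dependence.
- State that predictors are standardised and how the penalty is chosen.
- Add a note to Table 3 and its 6-month counterpart that the omitted measure is an exact combination of those retained, so its effect cannot be separated from theirs.

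If the models have already been run, report the scaling and penalty used and give the equivalent description beside the selected one.

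The cost is a few lines of text and no new data. The drawback is that the L1 penalty depends on the chosen set: an effect acting only through an omitted measure will appear as a combination of the retained ones and may be harder to detect. That is why the choice should rest on which constructs the investigators want to interpret.
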